 - To evaluate the impact of prophylactic belimumab on the incidence and severity of acute GvHD at 3 and 6 months after alloHCT
 - To evaluate the impact of prophylactic belimumab on overall survival at 6, 12 and 24 months after alloHCT
 - To evaluate the impact of prophylactic belimumab on relapse rate at 6, 12 and 24 months after alloHCT
 - To evaluate the impact of prophylactic belimumab on overall corticosteroid requirement (dose and duration) for treatment of chronic GvHD at 6, 12 and 24 months after alloHCT
 - To evaluate the impact of prophylactic belimumab on the necessity to use alternative treatment modalities for chronic GvHD at 6, 12 and 24 months after alloHCT
- Exploratory:
 - To evaluate the effect of prophylactic belimumab on post-transplant immune cell reconstitution.
 - To explore candidate biomarkers (i.e. BAFF level, BAFF:B cell ratio; B cell subpopulation frequency) that could predict subjects who may benefit from prophylactic administration of belimumab to prevent chronic GvHD.

Eligibility:

Key Inclusion criteria:

1. At least 18 years of age
2. ECOG performance status ≤ 2
3. Diagnosis of hematologic malignancy (i.e. acute myeloid leukemia, acute lymphoblastic leukemia, chronic lymphocytic leukemia, myelodysplastic syndrome, chronic myelogenous leukemia, Hodgkin's lymphoma, non-Hodgkin's lymphoma)
4. Use of myeloablative or non-myeloablative conditioning regimen
5. Use of mobilized peripheral blood stem cells from fully HLA-matched related or unrelated donor as a graft source

6. Acute GvHD prophylaxis with methotrexate and tacrolimus
7. Documented complete remission with full donor engraftment (by STR identity testing) on Day +30 bone marrow biopsy
8. Adequate end organ function:
 - Serum bilirubin $\leq 1.5 \times \text{ULN}$
 - Alanine aminotransferase (ALT) and aspartate aminotransferase (AST) $\leq 2.5 \times \text{ULN}$
 - Creatinine clearance $\geq 40 \text{ mL/min/1.73 m}^2$ by the Cockcroft-Gault formula
9. Women of childbearing potential must agree to use adequate contraception (hormonal or barrier method of birth control, abstinence) prior to study entry, for the duration of study participation, and for 16 weeks after the last dose of study drug. Should a woman become pregnant or suspect she is pregnant while participating in this study, she must inform her treating physician immediately.
10. Able to understand and willing to sign an IRB-approved written informed consent

Key Exclusion Criteria:

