1.2.4 Pharmacokinetics and Drug Metabolism

Pharmacokinetic Parameter	Population Estimates (n = 563)
Peak concentration (C_{max} , mcg/mL)	313
Area under the curve (AUC, day · mcg/mL)	3,083
Distribution half-life ($t_{1/2}$, days)	1.75
Terminal half-life ($t_{1/2}$, days)	19.4
Systemic clearance (CL, mL/day)	215
Volume of distribution (Vss, L)	5.29

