3 PATIENT SELECTION AND ENROLLMENT

3.1 Inclusion Criteria

1. At least 18 years of age
2. ECOG performance status ≤ 2
3. Diagnosis of hematologic malignancy (i.e. acute myeloid leukemia, acute lymphoblastic leukemia, chronic lymphocytic leukemia, chronic myelogenous leukemia, Hodgkin's lymphoma, non-Hodgkin's lymphoma, myelodysplastic syndrome, chronic myelomonocytic leukemia)
4. Use of myeloablative or non-myeloablative conditioning regimen
5. Use of mobilized peripheral blood stem cells from fully HLA-matched related or unrelated donor as a graft source
6. Acute GvHD prophylaxis with methotrexate and tacrolimus
7. Documented complete remission and full donor engraftment (by STR identity testing) on Day +30 bone marrow biopsy
 - a. Complete remission: less than 5% blasts in an aspirate bone marrow sample with a count of at least 200 nucleated cells, no blasts with Auer rods or persistence of extramedullary disease PLUS absolute neutrophil count (ANC) $> 1,500/\mu\text{L}$, platelet count $\geq 50,000/\mu\text{L}$ and no leukemic blasts in the peripheral blood.
 - b. Negative minimal residual disease
 - c. Full donor engraftment by STR testing (either by bone marrow or peripheral blood testing)
8. Adequate end organ function:
 - a. Serum bilirubin $\leq 1.5 \times \text{ULN}$
 - b. Alanine aminotransferase (ALT) and aspartate aminotransferase (AST) $\leq 2.5 \times \text{ULN}$
 - c. Creatinine clearance $\geq 40 \text{ mL/min/1.73 m}^2$ by the Cockcroft-Gault formula
9. Women of childbearing potential must agree to use adequate contraception (hormonal or barrier method of birth control, abstinence) prior to study entry, for the duration of study participation, and for 16 weeks after the last dose of study drug. Should a woman become pregnant or suspect she is pregnant while participating in this study, she must inform her treating physician immediately.
10. Able to understand and willing to sign an IRB-approved written informed consent.

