4.1 Confirmation of Patient Eligibility

All necessary procedures and evaluations must be performed to document that the subject meets all of the inclusion criteria and none of the exclusion criteria prior to first dose on Day 1. Adult subjects must read, understand, and sign the Institutional Review Board/Research Ethics Board/Independent Ethics Committee (IRB/REB/IEC) approved informed consent form (ICF) confirming his or her willingness to participate in this study before any study-specific screening procedures are performed. Subjects less than 18 years of age will not be enrolled on this study. Subjects must also grant permission to use protected health information per the Health Insurance Portability and Accountability Act (HIPAA).

Confirm patient eligibility by collecting the information listed below:

1. Registering MD's name
2. Patient's race, sex, and DOB
3. Three letters (or two letters and a dash) for the patient's initials
4. Copy of signed informed consent form
5. Completed eligibility checklist, signed and dated by a member of the study team
6. Copy of appropriate source documentation confirming patient eligibility

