5.5 Duration of Follow-up

Subjects will be followed after discontinuation of treatment every 3 months during the first 2 years post-C1D1 and then annually for 5 years post-C1D1 or until death, whichever occurs first. Subjects removed from study for unacceptable adverse events will be followed until resolution or stabilization of the adverse event.

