5.9 Women of Childbearing Potential

Women of childbearing potential (defined as women with regular menses, women with amenorrhea, women with irregular cycles, women using a contraceptive method that precludes withdrawal bleeding, and women who have had a tubal ligation) are required to have a negative pregnancy test within 7 days prior to the first dose of belimumab.

Women of childbearing potential must agree to one of the following:

- Complete abstinence from intercourse from 2 weeks prior to administration of the first dose of belimumab until 16 weeks after the last dose of belimumab (if consistent with the preferred and usual lifestyle of the patient). Periodic abstinence (e.g., calendar, ovulation, symptothermal, post-ovulation methods) and withdrawal are not acceptable methods of contraception.
- Consistent and correct use of one of the following acceptable methods of birth control for one month prior to the start of the study agent, during the study, and 16 weeks after the last dose of study agent:
 - Oral contraceptive, either combined or progestogen alone
 - Injectable progestogen
 - Implants of levonorgestrel or etonogestrel
 - Estrogenic vaginal ring
 - Percutaneous contraceptive patches
 - Intrauterine device (IUD) or intrauterine system (IUS) with < 1% failure rate as stated in the product label
- Male partner sterilization (vasectomy with documentation of azoospermia) prior to the female subject's entry into the study, and this male is the sole partner for that subject. For this definition, "documented" refers to the outcome of the investigator's/designee's medical examination of the subject or review of the subject's medical history for study eligibility, as obtained via a verbal interview with the subject or from the subject's medical records.
- Double barrier method: condom and occlusive cap (diaphragm or cervical/vault caps) plus spermicidal agent (foam/gel/film/cream/suppository)

If a patient is suspected to be pregnant, belimumab should be immediately discontinued. In addition, a positive urine test must be confirmed by a serum pregnancy test. If it is confirmed that the patient is not pregnant, the patient may resume dosing. If a female

patient or female partner of a male patient becomes pregnant during therapy or within one month after the last dose of belimumab, the investigator must be notified in order to facilitate outcome follow-up.

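### The pregnancy notification rule in Section 5.9 stops about 12 weeks before the protocol's own contraception period ends, and inclusion criterion 9 and Section 5.9 accept different contraceptive methods (minor)

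*Combined protocol and SAP*

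**What the plan says.** **Contraception period.** Inclusion 9 (Section 3.1, and likewise the synopsis) requires contraception "for the duration of study participation, and for 16 weeks after the last dose of study drug". Section 5.9 ends both the abstinence option and the listed-method option at 16 weeks after the last dose.

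**Notification.** Later in Section 5.9, the duty to notify the investigator arises when a female "patient or female partner of a male patient becomes pregnant during therapy or within one month after the last dose of belimumab". Its stated purpose is to allow follow-up of the outcome. Inclusion 9 adds a duty on the woman herself: if she becomes or suspects she is pregnant "while participating in this study, she must inform her treating physician immediately".

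**Supplier reporting.** Section 7.1.4 requires reporting of any pregnancy arising during study participation, within 2 weeks of learning of it, with no one-month limit. Participation is not defined. Under Section 5.5, subjects are "followed after discontinuation of treatment every 3 months during the first 2 years post-C1D1", then yearly to 5 years.

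**Methods.** The synopsis says "Women of childbearing potential must agree to use adequate contraception (hormonal or barrier method of birth control, abstinence) prior to study entry", and Section 3.1 has the same parenthesis. Section 5.9 instead obliges the woman to choose from a specific list. That list allows barriers only as a condom with an occlusive cap and spermicide, and it includes an IUD or IUS and a vasectomised sole partner.

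**The concern.** The protocol treats the 16 weeks after the last dose as a time when pregnancy should be avoided, but its only rule for notifying the investigator ends after about a quarter of that time. Staff working from Section 5.9 alone would not be told to ask for, or pass on, a pregnancy arising at, say, 10 weeks. For a male subject's partner at that point, no other section clearly applies.

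The method lists raise a separate eligibility question. Section 4.1 requires procedures to "document that the subject meets all of the inclusion criteria and none of the exclusion criteria prior to first dose", and inclusion 9 does not refer to Section 5.9. A woman using a single barrier could pass that check without meeting the mandatory list. A woman with a non-hormonal IUD could meet the list but not the wording of the criterion.

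**Working it through.** The plan gives no figure to reproduce here. The check is window arithmetic and a comparison of the texts.

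**1. Length of the gap.** Inputs: 16 weeks (inclusion 9, Section 5.9) and one month (Section 5.9), taken as 28 to 31 days.

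- Contraception period: 16 × 7 = 112 days.
- Outside the notification rule: 112 − 31 = 81 days to 112 − 28 = 84 days, or 11.6 to 12.0 weeks.
- Share covered: 28/112 = 25% to 31/112 = 28%.

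**2. Drug remaining, as context only.** Section 1.2.4 gives a terminal half-life of 19.4 days. Assume that it holds in transplant recipients and that decay is purely terminal-phase. The fraction remaining at day t is 2^(−t/19.4).

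- 28, 30 and 31 days: 36.8%, 34.2% and 33.0%.
- 112 days: 112/19.4 = 5.8 half-lives, leaving 1.8%.

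Sixteen weeks is consistent with wash-out, and one month is not. This concerns treated women only and supports no exposure claim for partners.

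**3. Which rule applies to a pregnancy 10 weeks after the last dose?**

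| Who | Section 5.9 | Section 7.1.4 and inclusion 9, if participation includes follow-up | If participation ends with treatment |
|---|---|---|---|
| Enrolled woman | No notice required | Both apply | Neither clearly applies |
| Partner of a male subject | No notice required | Inclusion 9 does not apply; 7.1.4 does not say | No clear rule |

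The text points both ways on participation. Sections 5.4 and 5.5 keep subjects under follow-up after treatment. But inclusion 9 adds 16 weeks on top of participation, which would be redundant if participation already covered years of follow-up. Section 5.8 also takes some subjects off study. For pregnancies that come to light after study completion, Section 7.1.4 requires only that an associated serious event judged possibly related be reported.

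**4. Can existing contacts carry a 16-week rule?** Section 10.2 schedules the last pregnancy test at +6 months, nominally 4 weeks after cycle 7.

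- Cycle 7 on time at week 20: the 16 weeks end at week 36. The +9-month contact falls at week 36 if 6 months is counted as 24 weeks, as the calendars do, or week 39.1 by calendar months.
- Every dosing window at its upper limit: 20 + (2 × 3 + 4 × 7)/7 = week 24.9. The period then ends at week 40.9, or week 42.9 with one two-week hold. Both fall before +12 months (week 48 or 52.2).

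**5. Methods compared.**

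| Method | Inclusion 9 | Section 5.9 |
|---|---|---|
| Pill, injection, implant, ring or patch | Accepted | Accepted |
| Hormonal IUS | Accepted as hormonal | Accepted, with a failure-rate limit |
| Non-hormonal IUD | Not named | Accepted, same limit |
| Vasectomised sole partner | Not named | Accepted |
| Single barrier | Accepted | Not accepted |
| Double barrier with spermicide | Accepted | Accepted |

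Three rows give different answers.

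**The case against.** A reader might infer that Sections 5.9 and 7.1.4 contradict each other. The documents do not support that. One concerns notice to the investigator and the other concerns reports to the supplier. Both can be followed, and Section 5.9 does not forbid later notice. Nor is it shown that late pregnancies in enrolled women would go unreported: if participation includes follow-up, Section 7.1.4 and inclusion 9 still apply.

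Nothing in the protocol requires the notification and contraception windows to be equal, and one month matches the 30-day adverse event window in Sections 7 and 8.1. That explains the choice. It does not explain why the rule meant to secure outcome follow-up ends well inside the period in which the protocol wants pregnancy avoided.

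It is also tempting to call the partner window an error. It is not one: no contraception period is set for men, so a longer partner window would be harmonisation only.

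On methods, inclusion 9 may be meant as a summary, with Section 5.9 giving the binding detail. On that reading a single-barrier user fails the protocol as a whole. Section 5.9 itself mentions study eligibility when describing how vasectomy is documented, and the eligibility checklist named in Section 4.1 is not in the documents. So it cannot be said that anyone would be wrongly enrolled. The objection does not remove the mismatch, because a summary should not accept what the detail rejects or leave out what it accepts.

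**Conclusion.** Two minor internal inconsistencies stand.

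- **Notification.** The Section 5.9 rule leaves 81 to 84 days of the 112-day contraception period uncovered. Against Section 7.1.4 this is a mismatch of scope. How well enrolled women are otherwise covered depends on the undefined meaning of study participation. Partners have no clearly stated rule after one month. The number of male subjects is not given and could be anywhere from 0 to 10.
- **Methods.** The two lists disagree on the single barrier, the non-hormonal IUD and the vasectomised sole partner.

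The textual differences and the gap in days are certain. The half-life figures rest on the assumptions stated with them and are not needed for the conclusion. With 10 subjects and a descriptive analysis, no endpoint, sample size statement or analysis is affected. The gain is clearer safety follow-up and a consistent eligibility rule.

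**What to change.** - **Section 5.9:** replace the one-month limit with at least 16 weeks after the last dose for female subjects, and use the same window for female partners of male subjects.
- **Section 7.1.4:** state that reporting covers at least this period whether or not the subject remains in follow-up, and say whether partner pregnancies are included. Wording it as a minimum matters, because 16 weeks would still be narrower than Section 7.1.4 if participation includes all follow-up.
- **Inclusion 9 (synopsis and Section 3.1):** replace the parenthesis "hormonal or barrier method of birth control, abstinence" with a reference to the methods listed in Section 5.9.

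The cost is wording in four places, a notification duty about 12 weeks longer, and one question at an existing quarterly contact. That contact is +9 months if the 16 weeks have ended by then, and otherwise +12 months. No visit or test is added. The protocol does not cap the number of dose holds, so the question should be tied to the actual last dose.

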5.10 Study Stopping Rule

As this is a pilot study enrolling 10 eligible participants, the study will be suspended if any death considered at least possibly related to study treatment occurs during participation. The suspension may be lifted only if review of the event by the PI and QASMC results in a recommendation to permit further study enrollments.

6 PHARMACEUTICAL INFORMATION

6.1 Belimumab (Benlysta) Description

Benlysta (belimumab) is a human IgG1 λ monoclonal antibody specific for soluble human B lymphocyte stimulator protein (BLyS, also referred to as BAFF and TNFSF13B). Belimumab has a molecular weight of approximately 147 kDa. Belimumab is produced by recombinant DNA technology in a mammalian cell expression system.

6.2 Clinical Pharmacology

Please refer to Section 1.2.

6.3 Pharmacokinetics and Drug Metabolism

Please refer to Section 1.2.

6.4 Supplier(s)

Belimumab will be provided free of charge by GSK.

6.5 Dosage Form and Preparation

Belimumab will be supplied as a sterile, white to off-white, preservative-free, lyophilized powder for intravenous infusion. It will be provided in single-use glass vials with a rubber stopper and a flip-off seal. Each 5-mL vial contains 120 mg of belimumab and each 20-mL vial contains 400 mg of belimumab. Upon reconstitution with Sterile Water for Injection, USP, each single-use vial delivers 80 mg/mL belimumab in 0.16 mg/mL citric acid, 0.4 mg/mL polysorbate 80, 2.7 mg/mL sodium citrate, and 80 mg/mL sucrose, with a pH of 6.5.

Dilution Instructions:

1. Dextrose intravenous solutions are incompatible with BENLYSTA. BENLYSTA should only be diluted in 0.9% Sodium Chloride Injection, USP. Dilute the reconstituted product to 250 mL in 0.9% Sodium Chloride Injection, USP (normal saline) for intravenous infusion. From a 250-mL infusion bag or bottle of normal saline, withdraw and discard a volume equal to the volume of the reconstituted solution of BENLYSTA required for the patient's dose. Then add the required volume of the reconstituted

- solution of BENLYSTA into the infusion bag or bottle. Gently invert the bag or bottle to mix the solution. Any unused solution in the vials must be discarded.
2. Parenteral drug products should be inspected visually for particulate matter and discoloration prior to administration, whenever solution and container permit. Discard the solution if any particulate matter or discoloration is observed.
 3. The reconstituted solution of BENLYSTA, if not used immediately, should be stored protected from direct sunlight and refrigerated at 2° to 8°C (36° to 46°F). Solutions of BENLYSTA diluted in normal saline may be stored at 2° to 8°C (36° to 46°F) or room temperature. The total time from reconstitution of BENLYSTA to completion of infusion should not exceed 8 hours.
 4. No incompatibilities between BENLYSTA and polyvinylchloride or polyolefin bags have been observed.

6.6 Storage and Stability

Vials of belimumab should be stored refrigerated between 2° and 8°C (36° to 46°F). Vials should be protected from light and stored in the original carton until use; it should not be frozen; exposure to heat should be avoided. It should not be used beyond the expiration date.

6.7 Administration

Belimumab will be given intravenously at a dose of 10 mg/kg over the course of one hour. Refer to the package insert for reconstitution instructions.

6.8 Special Handling Instructions

None.

7 REGULATORY AND REPORTING REQUIREMENTS

The entities providing oversight of safety and compliance with the protocol require reporting as outlined below. Please refer to Appendix G for definitions and Appendix H for a grid of reporting timelines.

Adverse events will be tracked from C1D1, as soon as the infusion of Belimumab, through 30 days following the last day of study treatment. All adverse events must be recorded on the toxicity tracking case report form (CRF) with the exception of:

- Baseline adverse events, which shall be recorded on the medical history CRF
- Adverse events that are less than CTCAE grade 3
- AEs not of special interest as defined in Section 7.1.4.1 (special interest AEs will be recorded regardless of grade, including those thought to be related to chronic GvHD)

Refer to the data submission schedule in Section 12 for instructions on the collection of AEs in the EDC.

Reporting requirements for Washington University study team may be found in Section 7.1.

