treatment may be associated with reduced steroid use and risk of severe flare. Belimumab is currently FDA approved for the treatment of systemic lupus erythematosus and another trial assessing the efficacy in rheumatoid arthritis has recently been completed. Furthermore, clinical trials in other rheumatologic conditions, such as scleroderma and Sjögren's syndrome [40] are underway [www.clinicaltrials.gov]. Treatment with belimumab plus standard of care was generally well tolerated with no apparent dose response in the safety profile. Rates of adverse events (AEs), severe AEs, serious adverse events (SAEs), AEs leading to discontinuation, and serious/severe infections were generally comparable to the rates observed in the placebo plus standard of care group. When used as a single agent there were rare grade ≥ 3 adverse events with the most common grade 1 or 2 adverse events involving infectious complications (i.e., upper respiratory infections, gastroenteritis, urinary tract infection), headaches, and neutropenia [37, 40]. Moreover, when belimumab was combined with standard of care immunosuppressive therapy in subjects with lupus, there was no increased rate of adverse events of any grade compared to standard of care plus placebo suggesting an acceptable benefit/risk balance of belimumab when combined with additional immune modulating agents [38, 39]. Psychiatric events, including depression and suicide, were observed more frequently with belimumab, although it is unknown if belimumab treatment is associated with increased risk for these events. Although no increase in the rate of serious infections or malignancies was observed, as with other immunomodulating therapies the mechanism of action of belimumab could increase the risk for these events. Hypersensitivity and infusion reactions were observed more frequently with belimumab, with anaphylaxis observed $\leq 1\%$ of subjects. The most commonly-reported adverse reactions, occurring in $\geq 3\%$ of patients receiving 10 mg/kg belimumab in clinical trials (and at a $\geq 1\%$ greater rate than placebo) were nausea, diarrhea, pyrexia, nasopharyngitis, bronchitis, insomnia, pain in extremity, depression, migraine, pharyngitis, cystitis, leucopenia, and gastroenteritis viral. Experience from open-label, long-term continuation trials of belimumab in SLE patients confirms prolonged treatment with belimumab remains generally well tolerated, with no apparent increase in the incidence rate of AEs or SAEs over time, including important events such as infections and malignancies [37, 41]. Long term belimumab treatment appears to provide sustained improvement in SLE disease activity and reduction of flares. Please refer to the investigator's brochure for summaries of clinical trials of belimumab.

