7.1.4 Reporting to GSK

In addition to events described in Section 7.4 as reportable, all events of possible drug-induced liver injury with hyperbilirubinemia defined as ALT \geq 3x ULN **and** bilirubin \geq 2x ULN (>35% direct) (or ALT \geq 3x ULN and INR > 1.5, if the INR is measured) termed ‘Hy’s Law’ events (INR measurement is not required and the threshold value stated will not apply to subjects receiving anticoagulants) should be reported.

Any pregnancy that occurs during study participation must be reported. To ensure subject safety, each pregnancy must be reported within 2 weeks of learning of its occurrence. The pregnancy must be followed up to determine outcome (including premature termination) and status of mother and child. Pregnancy complications and elective terminations for medical reasons must be reported as an AE or SAE. Spontaneous abortions must be reported as an SAE.

Any SAE occurring in association with a pregnancy, brought to the investigator’s attention after the subject has completed the study and considered by the investigator as possibly related to the study treatment, must be promptly reported to GSK.

Safety information should be sent via email notification **within 24 hours of awareness** for all SAEs and AEs of Interest, and within 60 days for any other reportable non-serious events to [contact] (backup [contact]).

7.1.4.1 Adverse Events of Special Interest:

The frequency of all (both serious and non-serious) of the following Adverse Events of Special Interest will be assessed and included in the final report:

- Serious Hypersensitivity or Infusion Reactions
- Serious infections, including herpes zoster and opportunistic infections
- Malignancy
- Suicidal thought, intent or behaviour

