12.1 Adverse Event Collection in the Case Report Forms

All adverse events that occur beginning with start of treatment (minus exceptions defined in Section 7.0) must be captured in the Toxicity Form. Baseline AEs should be captured on the Medical History Form.

Participant death due to disease progression should be reported on the Toxicity Form as grade 5 disease progression. If death is due to an AE (e.g. cardiac disorders: cardiac arrest), report as a grade 5 event under that AE. Participant death must also be recorded on the Death Form.

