13 STATISTICAL ANALYSIS

This trial is designed to allow preliminary assessments of safety/tolerability and efficacy of belimumab in the post-allogeneic stem cell transplant setting. No pre-specified hypothesis testing will be performed. All analyses of demographics, biological activity, and safety will be descriptive. A 90% exact binomial confidence interval will be constructed for preliminary efficacy information. Data obtained from correlative studies will be used to identify parameters associated with efficacy from belimumab treatment that will guide design of subsequent larger clinical trials. Age-, disease-, and donor-matched subjects will be used as an institutional control. These control subjects will be identified within the Bone Marrow Transplant and Lymphoma Tissue Bank (HRPO# 201103349). Presently, there are roughly 100 subjects with banked specimens and associated clinical outcomes data that will serve as the comparator in this study in assessing preliminary efficacy. The data from this study will be used for sample size calculation estimates of an expansion cohort in a subsequent phase II study. A total of N=10 patients will be enrolled for this study. Though the sample size was not determined based on statistical power, this would provide us reasonable precision on both safety and feasibility. Based on intensive simulation studies regarding the sample size for pilot and translational studies, Piantadosi (2005) recommends that a sample size of 10 to 20 patients be adequate to provide preliminary information. For safety assessment, for example, there would be 90% chance of observing at least 1 serious adverse event if the true rate is at least 20%. Conversely, there would be less than 10% chance that we would observe 2 or more serious adverse events if the true rate is less than 5%.

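### The adverse-event recording exceptions in Section 7 contradict each other and, as worded, keep grade 3–4 events not of special interest off the toxicity form; the scope of special interest is also undefined

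*Combined protocol and SAP*

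**What the plan says.** Section 8.1 makes safety and tolerability the primary endpoint, graded by CTCAE v4.03 from first treatment to 30 days after the last dose. It sets no grade cut-off.

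Section 7 starts from the rule that every adverse event goes on the toxicity form, then lists three exceptions as parallel bullets. The first is baseline events, which go on the medical history form. The second is "Adverse events that are less than CTCAE grade 3". The third is "AEs not of special interest as defined in Section 7.1.4.1 (special interest AEs will be recorded regardless of grade".

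Section 12.1 carries the same list into the data forms: "All adverse events that occur beginning with start of treatment (minus exceptions defined in Section 7.0) must be captured in the Toxicity Form". It adds that deaths, whether from disease progression or from an adverse event, are entered as grade 5.

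Section 7.1.4.1 defines special interest. Its lead-in says "The frequency of all (both serious and non-serious) of the following Adverse Events of Special Interest will be assessed". The first of its four items reads "Serious Hypersensitivity or Infusion Reactions", and the second is likewise limited to serious infections. The other two, malignancy and suicidality, carry no such limit. Section 5.7 uses the same narrow wording when it describes reporting to the drug supplier.

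**The concern.** The recording rule decides what the primary safety dataset contains. If it can be read in more than one way, two data coordinators following it faithfully would produce different datasets.

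Three things look wrong. The third exception has no grade limit, so taken as a separate exception it removes every event outside the four categories, and the grade threshold in the second adds almost nothing. The second and third exceptions disagree about low-grade events of special interest: one drops them and the other keeps them. And the definition on which the third exception depends contradicts its own lead-in.

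The events at stake matter for this drug and setting. Blood counts and chemistry are drawn every cycle (Section 10.1), so non-serious grade 3–4 laboratory abnormalities can be expected to come to light. Section 1.2.3 reports that with single-agent use "there were rare grade ≥ 3 adverse events with the most common grade 1 or 2 adverse events involving infectious complications", and names headache and neutropenia alongside them. It says separately that infusion reactions were more frequent with belimumab. The toxicity table in the semi-annual monitoring report goes to the institutional safety committee and, with the IND annual report, to the FDA (Appendix H), so an unclear rule could also affect oversight.

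**Working it through.** **Step 1: the plan's own figures.** Section 13 states that "A total of N=10 patients will be enrolled for this study" and that "there would be 90% chance of observing at least 1 serious adverse event if the true rate is at least 20"%. It also says that two or more serious events would be seen with under 10% probability if the true rate is below 5%.

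- At least one at 20%: 1 − 0.80^10 = 0.893. Stated 90%; reproduced.
- Two or more at 5%: 1 − 0.95^10 − 10 × 0.05 × 0.95^9 = 0.086. Stated under 10%; reproduced.

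Both figures concern serious events and presuppose that every one reaches the dataset analysed.

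**Step 2: what each reading puts on the toxicity form.** Reading A treats the bullets as separate exceptions, as they are set out. Reading B merges the second and third, so that only events both below grade 3 and not of special interest are omitted. Reading B is split by whether the serious-only items or the lead-in of Section 7.1.4.1 governs.

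| Event | A: separate | B: merged, serious-only items | B: merged, lead-in |
|---|---|---|---|
| Death | On (Section 12.1) | On | On |
| Grade 3–4, not of special interest, non-serious | Off | On | On |
| Grade 3–4, not of special interest, serious | Off the form; sent to the supplier | On | On |
| Grade 1–2 malignancy or suicidality event | Bullets disagree | On | On |
| Grade 1–2 non-serious infusion reaction or infection | Off, or bullets disagree, depending on Section 7.1.4.1 | Off | On |
| Grade 1–2, all others | Off | Off | Off |

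Two rows change with the reading in ways that matter most: non-serious grade 3–4 events outside the four categories, and grade 1–2 non-serious infusion reactions and infections. Non-serious herpes zoster and opportunistic infection fall under the same doubt. The last row is the same throughout; that is an openly stated threshold.

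**Step 3: do other sections restore the grade 3–4 events?**

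- Section 12.1 restores deaths only.
- Section 7.1.4 sends serious events, events of interest and a defined liver-injury pattern to the supplier. That is a reporting route, not a data-form rule. A grade 3–4 laboratory value need not be serious under Appendix G.
- Section 7.2 requires events exempt from expedited reporting to be captured electronically. The sentence follows a short list (planned or brief hospitalisation, respite care, disease progression) and names no form. Section 7 itself refers electronic collection to Section 12, which repeats the exceptions.
- Appendix H puts non-expedited events in the monitoring report's toxicity table but does not say how they are collected.

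None of these clearly restores a non-serious grade 3–4 event.

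**Step 4: size.** With 10 subjects, one subject is 1/10, or 10 percentage points of any subject-level rate. The documents give no rate for the affected events, so no expected loss can be computed. As a sensitivity check on Step 1 only, assume that the safety table is built from the toxicity form alone under reading A, and that a share f of subjects with a serious event have one recorded. The share f is an assumption. The chance of at least one recorded is 1 − (1 − 0.20f)^10:

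- f = 1.00: 89.3%
- f = 0.75: 80.3%
- f = 0.50: 65.1%
- f = 0.25: 40.1%

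Because serious events also reach the supplier, this range shows how far the stated figure depends on full capture. It does not estimate an actual loss.

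**The case against.** The best reply is that reading A defeats itself. If the bullets stood alone, the remark that special-interest events are recorded at any grade would clash with the bullet above it. That remark makes sense only as a carve-out from the grade threshold, so reading B is very likely what was meant, and under it all grade 3 or higher events are recorded. This stands as evidence of intent. It does not supply the missing rule: the text never joins the two conditions, and Section 12.1 imports the list as it is.

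A reader might also infer more than the documents support.

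- *That deaths are lost with the other high-grade events.* They are not. Section 12.1 requires them on the form, and its example, cardiac arrest, is outside the four categories.
- *That low-grade infusion reactions and infections are certainly lost.* They are lost only if the serious-only items override the lead-in. Section 5.7 leans that way, but the lead-in says the opposite, so this is an open contradiction.
- *That the primary endpoint cannot be estimated.* Serious events have their own route, reasons for stopping protocol therapy go on the case report forms (Section 5.4), and under reading B grade 3 or higher events and all special-interest events can be estimated. The only quantified safety statements concern serious events, and they reproduce.
- *That Section 1.2.3 describes low-grade infusion reactions as the usual profile.* The sentence on common grade 1–2 events names infections, headaches and neutropenia. Infusion reactions appear elsewhere, without a grade.

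Finally, limiting collection to grade 3 or higher plus special-interest events is a legitimate choice for a pilot. The objection is only that the text does not state that rule.

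**Conclusion.** The recording rule is wrong as written and should be corrected, because it governs the content of the sole primary endpoint. Read literally, it leaves grade 3–4 events outside four categories off the toxicity form. The non-serious ones, such as laboratory toxicities, have no other clear place in the data. It also contradicts itself on low-grade special-interest events, and it leaves undefined whether grade 1–2 non-serious infusion reactions and infections count.

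The conclusion rests on the wording of Sections 7, 7.1.4.1 and 12.1 and on the finding that Sections 7.1.4 and 7.2 and Appendix H do not clearly repair it. It does not rest on any assumed event rate. The number of events affected is unknown and could be none if site staff already apply the merged reading with the lead-in of Section 7.1.4.1. The protocol does not ensure that they do.

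**What to change.** 1. In Section 7, keep the baseline exception and replace the second and third bullets with one: adverse events that are both below CTCAE grade 3 and not of special interest are not recorded. Every event of grade 3 or higher, and every special-interest event of any grade, then goes on the form.
2. In Section 7.1.4.1, remove the word *Serious* from the first two items for data-form recording and frequency reporting, in line with the lead-in. State that the scope of 24-hour reporting to the supplier is unchanged, since that duty also refers to events of interest.
3. In Section 12.1, refer to the new rule in place of the general mention of exceptions.

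The cost is protocol wording, a form-completion instruction and slightly more data entry for 10 subjects. For subjects already treated, events noted at visits can be back-filled from source records.
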